4.1 Anticipated Clinical Benefits

Study participation may not provide any immediate benefit to study participants. However, results of this research may result in the following potential benefits to the study participants or to future diabetes patients:

- Development of an extended wear insulin infusion set
- Reduction in the number of required infusion set insertions/reduction of number of infusion sites
- Reduction in infusion site (skin/tissue) reactions
- Improved glucose control (e.g., more stable insulin kinetics)
- Improved CSII and insulin pump therapy options

4.2 Anticipated Adverse Device Effects

The anticipated adverse device effects (ADEs) for the Achilles infusion set are the same as those for commercially available CSII sets used by patients eligible for enrolment in this study. These are described in section 14 of this document. Commercial subcutaneous insulin infusion sets have a known failure rate of approximately 15–25% prior to their labelled 3-day (72 hour) wear duration. Therefore, T1DM patients are accustomed to frequent change outs with commercial infusion sets. In response to these known issues, the Capillary Biomedical Achilles infusion set incorporates a kink-resistant coil-reinforced soft polymer cannula. This cannula contains one distal and three proximal holes to ensure redundancy and extended wear-time of up to 7 days.

4.3 Residual Risks from Device Risk Analysis

The Achilles Infusion Set has been analysed for possible hazards using the methods in ISO 14971:2007 Medical Devices, Application of Risk Management to Medical Devices. The results of this risk analysis are summarized in section 6.1, Risk Analysis, of the Clinical Investigator's Brochure, manufacturer document 150-1073-00. Capillary Biomedical, Inc. considers the Achilles Infusion Set to be adequately safe to justify its use in clinical trials based on the benefits compared to overall risk.

4.4 Risks of Participation

This study includes T1DM participants that undergo routine diabetes treatment and glucose control methodology. A standardized study protocol, case report forms, study and investigational device use training will be provided to all study investigators/staff and study participants prior to any study related intervention or testing.

The study population consists of adult volunteer participants who have been diagnosed with T1DM, and have used an insulin pump for at least 6 months for basal and bolus insulin therapy to control their blood glucose. T1DM diagnosis will be confirmed at screening by c-peptide lab test.

Only insulin pump users with at least 6 months of experience with pump therapy will be enrolled to minimize the risk of pump use errors. Each potential study subject will be required to submit a minimum of 14 days of pump data to confirm pump use compliance. Patients who routinely wear their infusion set for >3.5 days will be excluded from participation to ensure a homogenous patient population of participants who adhere to infusion set labeling restrictions. Screening including physical exam, ECG and laboratory testing will rule out patients with anemia or known cardiovascular disease who may be at greater risk of procedure-induced anemia or whose hypoglycemia symptoms may be masked by concomitant medication.

The primary risks associated with extended wear of the Achilles infusion set are increased risk of hyperglycemic or hypoglycemic episodes and/or infusion site irritation or infection. To ensure patient safety while using the newly developed infusion sets, patients are required to wear a CGM sensor throughout the study. Only participants with previous CGM experience and willingness to wear a CGM will be recruited. The Dexcom G5 CGM should be set with alarm systems engaged throughout study duration. Study staff will be able to monitor each patient's interstitial glucose remotely and will be notified via text in case of alarm. Participants will be instructed to contact their study site for any issues.

Commercial subcutaneous insulin infusion sets have a known failure rate of approximately 15 - 25% prior to their labelled 3-day (72 hour) wear duration. Therefore, T1DM patients are accustomed to frequent change outs with commercial infusion sets. In response to these known issues, the Capillary Biomedical Achilles infusion set incorporates a kink-resistant coil-reinforced soft polymer cannula. This cannula contains one distal and three proximal holes to ensure redundancy and extended wear-time of up to 7 days.

Failure of the investigational Achilles infusion set may occur during the 7-day extended wear period. However, if Achilles infusion set failure occurs at any time during the home wear period, the subject will simply be instructed to change out the investigational device for their standard commercially available set to maintain CSII therapy. This is the same risk associated with a use of commercially available infusion sets.

CSII set infusion site irritation and infection are familiar risks to insulin pump users. The investigational Achilles infusion set will be manually inserted and secured (taped) to an appropriately selected body location by a trained study staff member. Participants will be observed at the study center for 3 hours to ensure initial Achilles infusion set function prior to

clinic discharge and start of home-use period. Study staff may attempt infusion set insertion three times. If insertion is not successful after 3 attempts, the Achilles infusion set is considered failed for this study subject.

Study participants will be instructed to check the Achilles infusion site for any skin abnormalities on a daily basis. All findings of skin irritation/infection (including tape reactions or cannula dislodgement) will be carefully monitored and recorded in a Patient Diary. If there is evidence of an infection at the infusion site, participants will be instructed to remove the infusion set and insert a fresh insulin infusion set as per their clinical routine. The Achilles infusion set will be placed in a provided container and biohazard bag. Participants are instructed to photograph the inflamed infusion site and contact the study staff via the provided study hotline.

As per routine pump therapy, participants will be instructed to closely monitor their blood glucose levels during the home wear period using standardized methods including SMBG, CGM, patient diaries, etc. Risks associated with extended Achilles infusion set/cannula use will be carefully monitored by the subject and study team, and documented daily in a patient diary. The insertion site will be visually inspected and photographed pre- and post-Achilles infusion set insertion. Emergency contact information will be provided in the case of Achilles device issues (site infection, infusion set failure, or need for cannula replacement). Any new risks identified during the study period will be promptly communicated to the investigational sites.

Alternate treatment with a commercial infusion set is available to study participants at any point during the feasibility evaluation and is not considered to increase subject risk. All other therapy will be conducted per standard of care for T1DM patients.

4.5 Potential Interactions

There are no known interactions between the materials used in the Achilles infusion set and possible concomitant medical treatments.

Based on the biocompatibility test report 150-1010-00 performed by the Medical Research Organization North American Science Associates, Inc (NAMSA®), it was concluded that “considering all gathered data, this risk assessment indicates that the likelihood of a toxic effect from Achilles Infusion Set is low. No further testing is recommended on this feasibility device.”

4.6 Risk Management Measures

The following measures will be taken to manage and minimize risk:

1. In-depth patient instructions, oral and written
2. 24/7 study helpline

3. Only include patients who have been using an insulin pump and rapid acting insulin for at least 6 months
4. One week run-in period (*Week 1*) with saline infusion through the Achilles infusion set to assess number of dislodged infusion sets and/or skin tolerability

4.7 Risk-to-Benefit Rationale

Insulin infusion sets fail early and fail often. Research from Stanford University found that the majority of infusion set failures are due to cannula kinking or a clogged insulin port (see Table 2).

Table 1: Infusion Set Failure Rate by Duration of Use

Day (s) of Use	Failure Rate
Day 1	> 15%
Day 3	> 25%
Day 7	> 65%

This high failure rate prevents wider adoption of insulin pump therapy that could improve current patient outcomes and expand pump access to users still depending on multiple daily manual injections.

Results from pre-clinical animal and bench studies of the Achilles infusion set design have shown a lower rate of cannula kinking (0% vs 57% in an equivalent commercial infusion set, $p < 0.001$) and improved infusion set functionality for extended use periods beyond 3 days. This study is designed to evaluate if similar results can be reproduced in human participants using routine insulin pump therapy for two extended use (up to 7 days) use wear periods of the Achilles infusion set. Participants will frequently monitor their blood glucose levels to ensure adequate glycemic control. Infusion set change out for any reason will be performed per standard therapy with no additional risk to the study subject or ongoing therapy.

5 Study Objectives

5.1 Primary Objective

The primary objective of this study is to evaluate feasibility and device performance of the Achilles infusion set over three extended home use wear periods of up to 7 days each during routine therapeutic insulin infusion.

5.2 Secondary Objectives

Secondary objectives include evaluation of:

- Standard glucose control measures obtained from Continuous Glucose Monitoring (CGM), including observed hyper- and hypoglycemic episodes
- Subject tolerability (subject comfort) during wear period
- Adverse events (infusion site reaction/infection, etc.)

5.3 Hypotheses to Test

This study is a first-in-human observational study of device feasibility in a known subject population. As such, there is no definitive relevant statistical hypothesis. A sample size was selected based on similar studies of insulin infusion set functionality (3,27,28).

5.4 Intended Performance/Success Criteria

Results of this study will be compared to those of Patel et al. (3), who observed that 30% of infusion sets performed adequately (no premature failure due to mechanical malfunction and no episodes of uncorrectable hyperglycemia prior to the end of 7 days of infusion set wear time), and, among infusion sets that did not exhibit mechanical malfunction, 60% performed adequately by the glucose control metrics for the 7-day wear period. Success criteria will be considered met if the Achilles infusion set exceeds these performance outcomes.

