1.4 Study Synopsis

1.4.1 Overview

This is a prospective, non-randomized, home-use feasibility study of device performance, usability, tolerability, and safety of an investigational infusion set for continuous subcutaneous

insulin infusion (CSII or insulin pump therapy) in up to 20 participants diagnosed with type 1 diabetes mellitus (T1DM). The Capillary Biomedical, Inc. (CapBio) Achilles infusion set is a sterile single use device designed to be used with commercially available infusion pumps (e.g., Medtronic MiniMed). The investigational Achilles infusion set contains a coil reinforced soft polymer indwelling cannula with one distal and three proximal holes (see item 2 Investigational Device).

The existing patient population at the study center will be screened for study eligibility within 21 days of planned study enrollment. Eligible participants will complete written informed consent and be assigned a study identifier.

The study is comprised of 3 periods. Each period is initiated at the study center and followed by a home-use phase of up to 7 days (Figure 1):

1. Week 1 (t = 7 days): Trial run with saline infusion. Patients will continue to use their own pump and insulin infusion set while wearing the CapBio Achilles infusion set connected to a second pump. The reservoir in this pump will be filled with saline and patients will mimic their insulin basal/bolus pattern on the dummy pump.
2. Week 2 (t ≤ 7 days): After successful completion of *Week 1*, patients will manage their blood glucose (BG) solely with their insulin pump and the Achilles infusion set. BG will be closely monitored with a continuous glucose monitoring (CGM) device. *Week 2* is considered complete when either, (1) an Achilles infusion set failure (see below) occurs and participant needs to insert a commercial CSII set to maintain routine therapy until they return to the study center, or (2) participant has worn Achilles for the total 7-day wear period.

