3. Week 3 (t ≤ 7 days): (**Note:** Initiation of *Week 3* will only occur if *Week 2* was completed without any major safety issues, adverse events or other concerns.) After completion of *Week 2* patients will return to study center to receive a fresh Achilles infusion set and continue BG management at home until infusion set failure (see below). BG will be closely monitored with a continuous glucose monitoring (CGM) device. *Week 3* is considered complete when either, (1) an Achilles infusion set failure occurs and participant needs to insert a commercial CSII set to maintain routine therapy until they return to the study center, or (2) participant has worn Achilles for the total 7-day wear period.

Infusion set failure is defined as:

1. The occurrence of unexplained hyperglycemia (glucose >250 mg/dL or >14 mmol/L) occurring more than 2 hours after a meal and not responsive to a pump bolus dose where response to the bolus is defined as a fall of at least 50 mg/dL (3 mmol/L) in blood glucose within one hour,

2. The occurrence of any hyperglycemic episode (glucose >250 mg/dL or >14 mmol/L) not associated with acute intercurrent illness, but with a concurrent ketone level ≥ 0.6 mmol/L.
3. Signs of infection (e.g. erythema or induration >1 cm in maximal diameter),
4. Occurrence of non-resolvable insulin pump occlusion alarm signal.

During home-use periods, participants will conduct daily visual infusion site inspection and record pain levels and skin reactions. They will use Dexcom G5 CGM (if patient is not routinely using this CGM) to monitor blood glucose and detect hypo-/and hyperglycemic episodes/events. If participant experiences an Achilles infusion set device issue, participants shall insert a commercial CSII set to maintain routine insulin therapy. Participants will be provided with training and written instructions if an Achilles device issue occurs at any time during home wear periods. They are instructed to contact study staff as early as possible after infusion set failure and return to the study site at their earliest convenience.

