7.1 General Approach

As a routine evaluation of the data during analysis, consistency of the study variables to properties of statistical tests will be checked. Descriptive statistics shall be used for independent variables.

For tabulated continuous variables, descriptive analyses will present the mean, standard deviation, median, minimum and maximum. For tabulated categorical variables, the number with the characteristic, the total number evaluated and the percent will be provided.

Unless otherwise specified, statistical analyses will be performed using vendor specified software products.

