7.2 Populations for Analysis

Intent-to-Treat (ITT) Analysis Population: All participants who meet all eligibility criteria and have undergone a first attempt to insert an investigational Achilles infusion set shall be included in the ITT analysis population.

Safety Analysis Population: All participants who had an investigational cannula inserted.

Per-Protocol (PP) Analysis Population: All patients who completed any part of the 7-day Achilles infusion set evaluation period.

The primary effectiveness analysis will be based on the ITT subject population. Sensitivity analyses of the primary effectiveness endpoint will be generated based on the PP population. The ITT population may contain some patients who did not complete the evaluation interval. This will require the use of imputation methods for missing values. Last observation carry forward will be used in such case.

The primary safety analysis will be based on the safety population. All secondary and exploratory effectiveness analyses will use both the ITT and PP populations.

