7.3 Analysis of the Primary Efficacy Endpoint

The primary study endpoint is the proportion of Achilles infusion sets that function each day of use, up to 7 days. This endpoint will serve as both the preliminary effectiveness and safety endpoint during the feasibility evaluation.

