7.7 Tabulation of Individual participant Data

Listings of the primary and secondary endpoints will be presented by patient and by time point for each treatment.

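### Section 5.4 declares success on observed percentages above 30% and 60% with no interval planned; a device exactly at those benchmarks would meet both about 34% of the time

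*Combined protocol and SAP*

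**What the plan says.** Section 5.4 takes two figures from a cited infusion-set study. In that study 30% of sets performed adequately to 7 days, with neither a mechanical malfunction nor uncorrectable hyperglycaemia, and 60% of the sets free of mechanical malfunction were adequate on glucose control. The rule follows: "Success criteria will be considered met if the Achilles infusion set exceeds these performance outcomes". No margin, test or confidence bound is attached.

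Section 5.3 says that "there is no definitive relevant statistical hypothesis" and that the sample size follows similar studies. Section 7.3 reads: "The primary study endpoint is the proportion of Achilles infusion sets that function each day of use, up to 7 days". For categorical variables section 7.1 promises that "the number with the characteristic, the total number evaluated and the percent will be provided", and section 7.7 adds: "Listings of the primary and secondary endpoints will be presented by patient and by time point for each treatment". No confidence interval appears anywhere in section 7.

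On who is analysed, section 7.2 makes the ITT population primary and says of incomplete evaluation intervals: "Last observation carry forward will be used in such case". Section 6.2.3 keeps participants who leave before finishing both 7-day periods in the ITT and per-protocol populations. Section 2.9 includes all data up to exit. Section 1.4.1 allows Week 3 only if Week 2 "was completed without any major safety issues, adverse events or other concerns".

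**The concern.** The protocol disclaims a hypothesis and, in the next section but one line of reasoning later, sets a pass/fail comparison with an external result. As written, the comparison uses the observed percentages alone. With at most 40 insulin sets those percentages are imprecise, so success could be declared, with no interval beside it, for a device that performs no better than the cited sets.

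A narrower gap concerns counting. The benchmarks are proportions of sets, and each participant can contribute two. Some participants will not start Week 3. Whether such a wear is left out of the denominator or filled in from Week 2 changes the percentage that is compared with 30% and 60%, and neither section 5.4 nor section 7.3 says which.

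**Working it through.** **Plan's own figure.** The sample of 20 participants (section 6.2.6) was chosen by precedent, with no alpha, power or effect size, so there is no calculation to reproduce.

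**Inputs**
- Benchmarks of 30% and 60%: section 5.4.
- Number of sets: 20 participants (6.2.6) × 2 insulin wears (1.4.1, Weeks 2 and 3) = 40. This is a maximum, because the synopsis says up to 20 and not every participant need start Week 3. Week 1 infuses saline and cannot contribute to the glucose outcome.
- Mechanically intact share at benchmark: not stated, but implied. Adequate performance requires no mechanical malfunction, so the share is 0.30 / 0.60 = 0.50.
- Assumed: independent sets, failure definitions that match the cited study's, both criteria required, and exceeding read as strictly greater.

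**Criterion 1 alone.** More than 30% of 40 means at least 13 sets. With X ~ Binomial(40, p):
- true p = 0.20: P(X ≥ 13) = 0.043
- true p = 0.30: P(X ≥ 13) = 0.423
- true p = 0.50: P(X ≥ 13) = 0.992

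**Both criteria.** Let M ~ Binomial(40, 0.50) be the intact sets and X given M ~ Binomial(M, 0.60) the adequate ones. Success needs X ≥ 13 and X/M > 0.60. Summing the exact probabilities over all (M, X) gives 0.344. With 20 sets, one per participant, it is 0.327. If exceeding is read as at least, the 40-set figure is 0.431.

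**Precision of a just-passing result.** The exact 95% interval for 13/40 (32.5%) is 18.6% to 49.1%. If 20 of the 40 sets were intact, 13/20 (65%) passes the second criterion with an interval of 40.8% to 84.6%. Both intervals include their benchmark.

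**Two sets per participant.** Simulating 20 participants × 2 sets, with within-participant correlation of 0 to 0.4 and everyone having Week 3, leaves the joint rate at 34% to 35%. No document gives a correlation.

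**Week 3 wears that never start.** The loss rate is assumed, and the range runs over correlation 0 to 0.4:

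| Participants with a Week 2 failure who have no Week 3 | Absent wear left out | Week 2 outcome carried forward |
|---|---|---|
| 10% | about 36% to 39% | about 29% to 32% |
| 50% (stress test only) | 37% to 48% | 14% to 23% |

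**Failure definition.** Sections 1.4.1 and 6.1.2 also list signs of infection as set failure, which the benchmark as described in 5.4 does not. If infection alone removed an assumed 5% or 10% of otherwise adequate sets, the joint rate would be about 26% or 18%.

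**The case against.** The strongest reply is that this is a first-in-human feasibility study which disclaims a hypothesis, attaches no stated decision or claim to the word success, and will publish counts and by-patient listings from which anyone can compute an interval. The rule also works as a screen: a device at a true 20% passes the first criterion only 4% of the time, and one at 50% passes 99% of the time. All of that stands, and it limits the weight of the point. It does not remove it, because the protocol itself commits to a declaration against an external figure and plans nothing beside that declaration to show its precision.

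Four stronger readings are tempting and are not supported.
- A reader might treat the 34% as an inflated type I error. No alpha is stated, so none is breached.
- A reader might vary the intact share from 45% to 55% and quote a joint rate of 24% to 42%. With glucose success held at 60%, those devices perform at 0.45 × 0.60 = 27% and 0.55 × 0.60 = 33% overall, so they are not at benchmark.
- A reader might say that the denominator is undefined. Sections 2.9, 6.2.3 and 7.2 settle which participants are analysed. Only the set-level treatment of a Week 3 wear that never began is open.
- A reader might expect heavy, failure-driven loss of Week 3. A failed Week 2 set does not itself bar Week 3: section 2.9 counts Week 2 as complete on set failure and brings the participant back, and three failed insertions on Day 0b still allow Day 0c. The Week 3 condition in 1.4.1 concerns safety issues, adverse events and other concerns. Losing half of those with a Week 2 failure would remove 0.70 × 0.50 = 35% of Week 3 wears, which nothing in the documents suggests.

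It is also fair to say that allowing for clustering matters little for the joint pass rate, and that a plain exact interval with a caveat would serve nearly as well if correlation is low.

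**Conclusion.** The point holds as a cheap improvement to what the trial can conclude. Under the current text, a device exactly at both benchmarks would be reported as meeting the success criteria about 34% of the time, and would pass the 30% criterion alone 42% of the time. These figures rest on 40 independent sets, matching failure definitions, a strict reading of exceeding, and the 50% intact share implied by the two benchmarks. Fewer sets or within-participant correlation change the joint figure little. Counting infection-only failures would lower it. With a modest assumed Week 3 loss of 10% after a Week 2 failure, the open counting choice moves it to about 36% to 39% or about 29% to 32%. The change is recommended, not essential: without it the trial remains a sound feasibility study, but its success statement would say more than the data can carry.

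**What to change.** Amend sections 5.4 and 7.3 as follows.
1. Report both Day-7 proportions with two-sided 95% confidence intervals that allow for two sets per participant, or exact intervals with a caveat about the pairing. Show Week 2 sets alone, one per participant, as a check.
2. State that a Week 3 wear that never started is left out of the set-level denominator, with a sensitivity row that carries the Week 2 outcome forward. State whether failures due to infection alone count against the 30% and 60% criteria.
3. Keep the numerical criterion as a feasibility go/no-go. Report a result whose interval includes the benchmark as numerically above benchmark, not as evidence of better performance than the cited study.

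Clearing the lower limits should not become a mandatory test. With 40 independent sets, an exact lower limit above 30% needs 19/40 (47.5%), which a device at a true 50% reaches only about 68% of the time.

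The cost is SAP wording, two intervals and two extra table rows, with no change to design or sample size. The downside is a less favourable claim: an interval from 40 or fewer sets will often include the benchmark even for a good device, and the Week 2 check is wide (7/20 gives 15.4% to 59.2%).
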